#### **7.3.1 Rescue Medication**

Rescue medication will be permitted after completion of the 2 hour assessments if the migraine does not respond (subject is not headache pain free). If the migraine does not respond within 2 hours a second dose of randomized study drug may be taken up to 24 hours after the first dose as long as no other rescue medication has been used. The Investigator may advise each subject as to an alternative suitable rescue medication. Triptans, ergots, opioids and barbiturates **MUST NOT** be used for rescue medication within 24 hours of study drug administration. The use of rescue medication will be recorded in the subject diary.

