### 10.5.1 Primary Analysis

The treatment effect between lasmiditan and placebo will be tested first for the primary endpoint of the proportion of subjects who are headache pain free and the key secondary endpoint of the proportion of subjects who are MBS free at 2 hours in the mITT population between the lasmiditan 200 mg and placebo dose group based on the first dose. The primary analysis will be completed using logistic regression Wald Chi-square test with a basic model including treatment group and region, using a one-sided test at the  $\alpha=0.025$  level of significance.

If the primary analysis is statistically significant (one-sided,  $p<0.025$ ), additional confirmatory hypotheses will be tested on the proportion of subjects who are headache pain free and the proportion of subjects who are MBS free at 2 hours in the lasmiditan 100 mg and placebo

groups followed by the lasmiditan 50 mg and placebo groups.

Headache pain free at 2 hours will be defined as a reduction in headache severity from moderate (2) or severe (3) at baseline to none (0) two hours after dosing with study drug. MBS free at 2 hours will be defined as a 'no' response to the presence of the symptom (either nausea, phonophobia, or photophobia) that was identified as MBS at predose, 2 hours after dosing with study drug.

A qualifying migraine is defined as a migraine treated with study drug within 4 hours of onset.

Subjects taking rescue medication within the first two hours or who fail to record headache severity at 2 hours will be assumed to have no headache response in the mITT and the ITT analyses.

A subject is defined to have used rescue medication within the first two hours post dosing if at least one medication is documented in the rescue medication log in the subject electronic diary for which:

$0 \text{ (min)} < \text{date/ time rescue medication (diary)} - \text{date/ time of dosing (diary)} < 120 \text{ (min)}.$

Subjects who do not provide a headache pain severity rating at baseline or who use other medication prior to the study drug for the study migraine attack will be assumed to have no headache response for the ITT analysis.

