##### **10.6.1 Analysis of second dose for rescue**

A second dose of study drug will be considered rescue medication if taken by a subject that did not achieve headache pain free at 2 hours and completed the 2 hour assessments prior to taking the second dose.

Summary statistics will be presented by treatment sequence on relief of migraine symptoms (pain free and MBS free) along with the time course to headache relief explored up to 48 hours. Subjects that use an alternative rescue medication will not be included in the summary statistics of response to treatment for rescue.

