5.2 Analysis of First and Second Doses

Any analyses based on first dose will only include data observed up to the time of dosing with a second dose. These summaries will be presented based on the first dose taken. The exception to this is the primary and secondary endpoints at the 2-hour time point; if a second dose is taken before the 2-hour time point, the subject will still be included in the summary at 2 hours and will be analysed as having not achieved headache pain-free or MBS-free status at 2 hours.

Any analyses based on the second dose will only include data observed on or after the time of dosing with a second dose. These summaries will be presented by treatment sequence, listed in Section 2.3. Analyses based on the second dose will be done for both the rescue and recurrence subpopulations.

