11.2 Primary Efficacy Analysis

The primary efficacy analysis will test the treatment effect, between lasmiditan 200 mg and placebo, of the primary efficacy endpoint of the proportion of subject's headache pain-free at 2 hours post-dose. This analysis will be presented by treatment group, based on the first dose.

Headache pain-free is defined as a reduction in headache severity from mild (1), moderate (2), or severe (3) at baseline to none (0).

Subjects who do not provide a headache pain severity rating at baseline, or who do not provide a headache pain severity rating at the two-hour time point will be assumed to have not achieved headache pain-free.

Subjects taking any rescue medication within the first two hours will be assumed to have not achieved headache pain-free. Subjects who use other medication prior to the study drug to treat the migraine attack will also be assumed to have not achieved headache pain-free.

Subjects who treat a no (0) severity migraine will not be included in the primary analysis. Sensitivity analyses, as described in Sections 11.4, 11.5 and 11.6 will also be performed for the primary endpoint on the mITT population.

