11.3 Key Secondary Efficacy Analysis

The key secondary efficacy analyses will test the following:

- The treatment effect, between lasmiditan 200 mg and placebo, of the key secondary efficacy endpoint of MBS-free at 2 hours post-dose.
- The treatment effect, between lasmiditan 100 mg and placebo, of the key secondary efficacy endpoint of headache pain-free at 2 hours post-dose.
- The treatment effect, between lasmiditan 100 mg and placebo, of the key secondary efficacy endpoint of MBS-free at 2 hours post-dose.
- The treatment effect, between lasmiditan 50 mg and placebo, of the key secondary efficacy endpoint of headache pain-free at 2 hours post-dose.
- The treatment effect, between lasmiditan 50 mg and placebo, of the key secondary efficacy endpoint of MBS-free at 2 hours post-dose.

MBS-free is defined as the absence of the associated symptom of migraine (either nausea, phonophobia, or photophobia) at 2-hour post-dose that was identified pre-dose as the most bothersome symptom. Subjects who record that no symptoms were present at baseline will be

excluded from the key MBS analyses. Likewise, subjects who treat a migraine of no (0) severity will not be included in the key analysis of headache pain. Such subjects will also be excluded from the table produced for the sensitivity analysis described in Section 11.5, but not from the programming steps that impute missing MBS data.

Subjects who do not provide a symptom rating at baseline will be considered as follows:

- Subjects who record at least one symptom present at baseline, but who do not designate one as most bothersome, will be treated as if all symptoms present are most bothersome and will be considered MBS-free at any time point post-dose only if all symptoms present at baseline are no longer present at that time point.

Subjects taking rescue medication within the first two hours, or who fail to record a symptom rating at 2 hours, will be assumed to have not achieved MBS-free. Subjects who use other medication prior to the study drug to treat the migraine attack will also be assumed to have not achieved MBS-free.

The counts and percentages of which symptom was chosen as the most bothersome symptom will also be presented.

These analyses will be presented by treatment group, based on the first dose.

Sensitivity analyses, as described in Sections 11.4, 11.5 and 11.6 will also be performed for the key secondary endpoints on the mITT population.

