11.7.1 Headache Pain-Free

The endpoint of headache pain-free will be summarized at the 0.5, 1, 1.5, 3, 4, 24, and 48-hour post-dose time points. This summary will be presented by treatment group for the ITT, mITT, and PP populations, based on first dose.

Subjects who had a mild, moderate, or severe headache at the time of dosing will be the reference subjects for this summary. Subjects missing a headache severity at baseline will not be summarized. Subjects missing a severity assessment at a post-dose time point will not be counted as pain-free.

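### After 2 hours, the exploratory first-dose pain-free, MBS-free and relief results have no rule for non-study rescue medication, so relief that follows another drug can count as a first-dose response

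*SAP*

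**What the plan says.** - **Rescue after 2 hours.** Under Protocol 7.3.1, a subject who is not pain-free and has completed the 2-hour assessments may take the second study dose (up to 24 hours, if no other rescue has been used) or a different drug: "The Investigator may advise each subject as to an alternative suitable rescue medication". Triptans, ergots, opioids and barbiturates are barred for 24 hours.
- **Where first-dose data stop.** SAP 5.2: "Any analyses based on first dose will only include data observed up to the time of dosing with a second dose". The second dose here is study drug. In the e-diary description (SAP 5), reporting that dose cancels the remaining first-dose alarms. Taking another drug is not said to do so.
- **Rescue rules at 2 hours.** For pain-free, SAP 11.2 says: "Subjects taking any rescue medication within the first two hours will be assumed to have not achieved headache pain-free". For MBS, SAP 11.3 says: "Subjects taking rescue medication within the first two hours, or who fail to record a symptom rating at 2 hours, will be assumed" not to be MBS-free.
- **Later time points.** SAP 11.7.1 says only: "Subjects missing a severity assessment at a post-dose time point will not be counted as pain-free". SAP 11.7.3 and 11.7.5 leave subjects with missing data out of that time point. SAP 11.7.6 to 11.7.8 censor subjects without an event at their last assessment up to 24 hours. None of these sections mentions other medication.
- **Where the plan does account for it.** Sustained pain-free (SAP 11.7.2) requires that no medication was used after the first dose. SAP 11.7.10 tabulates rescue and recurrence medication by arm and time window.

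**The concern.** Take two subjects, both still in pain at 2 hours. One takes the second study dose, and the later scores leave the first-dose analysis. The other takes a permitted analgesic, keeps answering the first-dose diary, and reports no pain at 24 hours. The second subject is pain-free at 24 hours in SAP 11.7.1 and an event in SAP 11.7.6. The choice of rescue drug, not the effect of the first dose, decides how they are counted.

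The time course of the effect on pain and MBS is the whole of the secondary objective (Protocol 5.2). Unless stated otherwise, exploratory efficacy hypotheses are tested at two-sided 0.05 (SAP 11). Readers will take the late rates and curves as the effect of the first dose, although beyond 2 hours they mix it with whatever rescue followed. The per-protocol tables do not remove the problem: SAP 4.2 excludes rescue before 2 hours and prohibited drugs within 24 hours, but not permitted rescue taken later.

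**Working it through.** **1. The rules side by side.** I read data cut under SAP 5.2 as missing in the sections that follow.

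| Result | Second study dose after 2 h | Other drug after 2 h |
|---|---|---|
| Pain-free at 3, 4, 24, 48 h (11.7.1) | Later data cut; not pain-free | Observed score used |
| MBS-free at 3, 4, 24, 48 h (11.7.3) | Later data cut; out of the denominator | Observed score used |
| Relief after 2 h (11.7.5) | Later data cut; out of the denominator | Observed score used |
| Kaplan-Meier times (11.7.6-11.7.8) | Censored at last assessment before the dose | Followed to 24 h; a later response is an event |
| Sustained pain-free (11.7.2) | Not sustained | Not sustained |

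SAP 11.7.5 also reports relief at 2 hours without an early-rescue rule. Protocol 10.5.1, which assigns no headache response after rescue in the first two hours, arguably covers that case.

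**2. The plan's own figure.** The documents give no figure for rescue. The nearest is the power for 2-hour pain-free in SAP 2.2: above 90% for each dose, with 570 per arm and one-sided 0.025. A pooled-variance normal approximation with rates of 7.4% (placebo), 13.9% (50 mg), 13.6% (100 mg) and 18.8% (200 mg) gives 94.6%, 92.8% and 99.99% for 50, 100 and 200 mg. The figure reproduces, so I use the same rates below.

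**3. Subjects eligible for rescue at 2 hours.** Placebo: 1 - 0.074 = 92.6%. Lasmiditan 200 mg: 1 - 0.188 = 81.2%.

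**4. Illustration with equal uptake.** Let r be the share of those subjects who take non-study rescue and q the share of these who are pain-free afterwards. Both are assumptions. With everything else held at its 2-hour status:

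late rate = p + (1 - p) × r × q

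When r and q are equal across arms, the difference becomes 11.4 × (1 - r × q) points.

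| r | q | Placebo | 200 mg | Difference (points) | Odds ratio |
|---|---|---|---|---|---|
| 0 | any | 7.4% | 18.8% | 11.4 | 2.90 |
| 10% | 20% | 9.3% | 20.4% | 11.2 | 2.52 |
| 20% | 40% | 14.8% | 25.3% | 10.5 | 1.95 |
| 30% | 60% | 24.1% | 33.4% | 9.3 | 1.58 |

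Over the same range, the 50 mg difference goes from 6.5 to between 6.4 and 5.3 points, and the 100 mg difference from 6.2 to between 6.1 and 5.1.

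**5. Unequal uptake, q = 40%.**
- 30% on placebo, 20% on 200 mg: (0.188 + 0.812 × 0.08) - (0.074 + 0.926 × 0.12) = 0.253 - 0.185 = 6.8 points.
- 20% on placebo, 30% on 200 mg: (0.188 + 0.812 × 0.12) - (0.074 + 0.926 × 0.08) = 0.285 - 0.148 = 13.7 points.

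Placebo gains more only while r × q on 200 mg is below 0.926 / 0.812 = 1.14 times its value on placebo.

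**The case against.** The strongest reply is that every affected result is exploratory and that the plan already reports a medication-free late endpoint (sustained pain-free) and rescue use by arm. Reporting observed status regardless of rescue, beside those tables, is a recognised choice. That lowers the priority of the point. But the plan does not state that choice, and it does not apply it consistently: it cuts data at one form of rescue and not at the other.

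Three stronger readings are tempting, and the documents do not support them.

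- **That the 2-hour results are contaminated.** They are not. SAP 11.2 and 11.3 make rescue within two hours a non-response, SAP 5.2 does the same for an early second dose, and permitted rescue comes after the 2-hour assessments.
- **That rescue users are counted as responders as such.** Their observed score is used. They count only if they then meet the response definition, and some might have improved without rescue.
- **That the SAP silently drops a protocol exclusion for the second dose.** Protocol 10.6.1 says: "Subjects that use an alternative rescue medication will not be included in the summary statistics of response to treatment for rescue". The natural meaning of alternative is a drug taken instead of the second study dose: Protocol 7.3.1 allows that dose only if no other rescue was used, Protocol 9.1.8 sets the two side by side, and Protocol 10.6.2 confines its summary to second-dose users. On that reading SAP 4.1 agrees with the protocol and SAP 5.1 has no change to declare. What stands is narrower: SAP 11.7.13 to 11.7.18 have no rule for another drug taken after the second dose.

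A practical objection also has force. SAP 4.2 notes that concomitant medications on the CRF carry start dates without times, so the fix needs a fallback when the diary time is missing.

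**Conclusion.** The gap is real and worth closing before unblinding. It is confined to exploratory first-dose results after 2 hours; the confirmatory tests do not change. Under equal uptake and success within the assumed ranges, the late 200 mg difference is diluted modestly, from 11.4 to between 11.2 and 9.3 points. This rests on carrying the 2-hour planned rates forward and on attributing every pain-free report after rescue to the rescue drug.

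A reader might infer that placebo must gain most, by a large amount, or that the late difference could reverse. More placebo subjects are eligible for rescue, so dilution is the plausible direction, but the documents give no non-study rescue uptake by arm. Even 40% uptake on placebo against 25% on 200 mg, with half of users pain-free, gives 0.926 × 0.40 × 0.5 = 18.5 points against 0.812 × 0.25 × 0.5 = 10.2, which leaves a difference of about 3.0 points and no reversal. Higher uptake on 200 mg can widen the difference, as step 5 shows. The firm conclusion is that late effects cannot be attributed to the first dose, not that they are biased by a known amount.

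**What to change.** - **SAP 5.2.** Add that, from the recorded time of any non-study medication taken for the migraine, the subject counts as not pain-free, not MBS-free and not relieved at all later first-dose time points. If the time is missing, apply the rule from the first assessment with a Yes to the diary question on other medication, which SAP 11.7.10 already uses.
- **SAP 11.7.6 to 11.7.8.** State that a response first reported after such medication is not an event. Fix the handling before unblinding: either event-free to 24 hours, which matches the rule above, or censored at rescue, which treats subjects who needed rescue as if they had the same outlook as those who did not.
- **SAP 11.7.13 to 11.7.18.** State the same rule for other medication taken after the second dose.
- **SAP 5.1.** List the rule.

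The cost is wording and one extra derivation. Protocol 9.1.8.1 already has the date and time of rescue recorded, and Protocol 10.5.1 already relies on a rescue log in the diary. Late response rates will fall somewhat in every arm. The 2-hour primary and key secondary results stay the same.

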5.3 Handling of Missing Values

Subjects who fail to record information at a particular analysis time point will have that value considered missing in the respective table, unless otherwise specified.

The primary and key secondary endpoints of headache severity and MBS presence at 2 hours post-dosing are two exceptions to this: (1) Subjects who fail to record a headache severity at 2 hours will be assumed to have not achieved headache pain-free, and (2) subjects who fail to record the absence of a symptom at 2 hours that was considered their MBS at baseline will be assumed to have not achieved MBS-free. A sensitivity analysis for missing data under alternative assumptions will be performed, as described in Section 11.5.

5.4 Derivation of Electronic Diary Assessment Times for Efficacy and Exploratory Analysis

Primary and secondary efficacy endpoints along with second-dose exploratory analysis endpoints will be summarized at various elapsed times following dosing. The endpoints will depend on data collected by an e-diary that requires a subject's response entries in the correct order and at the expected, scheduled assessment times. These assessment times are calculated by the e-diary from elapsed time since dosing. (They will not be recalculated as a part of analysis programming.) The e-diary poses questions to be answered within a pre-specified window of elapsed time after dosing. There will be some scenarios when responses appear to have been limited by the e-diary programming, if questions are not answered in the expected order or during the programmed window, which may cause unscheduled data at some time points.

Unscheduled data can be defined as invalid data at time points which do not correspond to the actual dosing data at the intended time point entered by subject. Listed are some examples of unscheduled data:

1. When subject takes 2nd dose but due to subject's response to the timing of dosing question in e-diary, the e-diary does not understand that subject took 2nd dose, but continues to collect the first dose time points because they are still 'valid' based on subject's entry. Thereby second dose questions do not become available until the time points align. In this case, the data for first dose is unscheduled.
2. Due to subject's responses to e-diary questions, e-diary assumes that subject took 2nd dose at one-time point but subject indicates dosing at a different time point. This makes their second dose data unscheduled but often keeps first dose data from being unscheduled.
3. Due to subject's responses to e-diary questions, e-diary assumes that subject took 2nd dose but subject indicates not dosing as per study drug accountability and CRF confirmation so 2nd dose data will be unscheduled.

Some specific scenarios are listed below for derivation of analysis time points for efficacy and exploratory endpoints.

1. Retroactive dose entry. If a subject enters the time of a dose retroactively, rather than at the time of taking the dose, the recorded time, and potentially date, of the second dose may be before some or all of the scheduled times of assessments that would otherwise have appeared to be associated with the first dose. In those cases, the apparent first-dose assessments after the recorded time of the second dose, and the second-dose assessments at times calculated from the retroactively entered dosing time will not be included in efficacy analyses.
2. Reports intention to take second dose, without confirmation. Subjects report their intention to take a second dose but may not *confirm* having done so in e-diary. Even if indications of taking second dose are observed in e-diary data, until the entry shows confirmation of second dose times, the e-diary will not have a confirmed second-dose time from which to calculate post-dose assessment times after that second dose, and it will not switch to second-dose mode. In this state, second-dose assessments will be missing. Additionally e-diary continues to collect first dose data although the subject may have taken second dose. Even if use of a second dose is recorded on the on CRF, the related second-dose assessments may not be available in the e-diary because the e-diary is not working in second-dose mode; hence, the exploratory endpoints for second dose will not

be available at those analysis times. Additionally, first dose assessments collected after this time will be considered unscheduled.

3. Multiple reports of a migraine - complicated by aura. If a subject reports a migraine, but does not indicate taking first dose at a specific time due to presence of aura, the efficacy and exploratory analysis endpoints for first and second dose will be summarized for the migraine, which has the reference for most recent available treated migraine data at analysis time points.
4. Missing first dose dates and associated assessments in e-diary. If the first dose is reported taken in the CRF with the appropriate date entered in CRF but the subject did not complete the e-diary for assessments, then the date of first dose and associated assessments will be missing in e-diary data. These subjects (e.g. lost to follow-up) will not be included in appropriate populations of efficacy analysis.
5. Missing second dose date and associated assessments in e-diary. If a second dose is reported taken in CRF with appropriate date entered in CRF but the subject is not able to complete e-diary for assessments, then the date and associated assessments of second dose will be missing in e-diary data. These subjects might not be included in appropriate populations of efficacy analysis based on the timing of second dose with respect to first dose. For purposes other than timed efficacy assessments, first and last dates of exposure to treatment will be identified from CRF sources as described in Section 5.
6. First and second dose dates and times in e-diary do not match CRF dates and times. Subjects may have entered dates and times in the e-diary that do not match dates and times ultimately entered in the CRF (data entered in Inform by sites based on subject's recall of dosing). The screens for post dose assessments entered by subjects are auto-generated by the e-diary at times with respect to dosing dates and times entered in the e-diary. As a result of this e-diary function, these subjects will be included in appropriate populations of efficacy analysis with respect to e-diary dates and times and their relative post-dose assessments times. Data handling rules in these cases are listed in Appendix 16.3.

Some additional scenarios under this category are listed as points a. and b. below.

- a. Subjects which indicates that the CRF dates are most appropriate but different than e-diary and can be confirmed with e-diary assessment times, CRF dates will be considered over e-diary dates. For example, subject initially reports in the e-diary that they took second dose at the same time as first dose. However, when they return to site at visit 2 and report their mistake and provide the correct dosing information to be recorded in the CRF the corrected time allows us to preserve first dose assessment data. In those cases, subjects second dose data will be considered as unscheduled and first dose efficacy assessment will be used for appropriate populations of efficacy analysis based on CRF date and times.
- b. For subjects with different e-diary and CRF times, if the e-diary assessments are done retroactively as in Scenario #1, CRF time will be compared with e-diary time. Subjects with the time difference of less than 1 hour will be included in appropriate populations of efficacy analysis for first dose. Subjects with the time difference of greater than 1 hour will be included in appropriate populations of efficacy analysis with the assumption e-diary assessments are correct on CRF. These subjects will be removed from additional sensitivity analysis as described in Section 11.6 for primary and key secondary analysis.

7. Treating more than one migraine, or taking second dose too late. If a subject treats two distinct migraines with the first and second doses or takes the second dose later than 24 hours after first dose, the date and times for second dose assessments will not be available for recording assessment results in the e-diary. As in Scenario #4 and #5 above, for these subjects, the date of the last dose date for purposes other than timed efficacy assessments will be identified from CRF data as described in Section 5.
8. Subjects reporting migraine start time or dosing time in future in e-diary. If a subject reports a migraine start time in the future and if the time reported is less than one hour in the future, this will be considered as minor minute or hour entry issues and the migraine start time will be set as time of collection. The remaining time issues will be assumed on visual confirmation as AM/PM (midnight/noon) and PM/AM (yesterday/today) entry issues then these will be rolled back by increments of 12 hours until the time is before time of data collection. After these corrections if migraine start is still after dosing time then the migraine start time is set to dosing time. These subjects will be included in the appropriate populations of efficacy analysis with these assumptions but will be removed from additional sensitivity analysis as described in Section 11.6 for primary and key secondary analysis.
 - a. Similarly for subjects who report a first dose time with start in the future (by several hours) than indicated dosing with question “Treating Migraine with Study Med now” as “Y” at the migraine pain begin time, their efficacy assessments for first dose will be those many hours ahead of the actual assessment time for severity reporting. For example, e-diary’s 0.5 hour time point is actually 7.5 hours if the first dose time is after 7 hours of the reported migraine start time. If the reported dose time is less than 10 minutes than the time of reporting migraine as in the stated question, then these will be ignored and subject’s efficacy assessments will be used for appropriate populations of efficacy analysis. All other subjects with time difference of greater than 10 minutes will be excluded from the appropriate populations of efficacy analysis.
9. Subjects with partial second dose time on CRF and no e-diary date and time for second dose Subjects who are able to enter the first dose assessment data in e-diary but they are not able to complete the e-diary for second dose. These subjects will be able to give second dose confirmation date on the CRF at site for visit 2 but may not remember the time of the dosing for second dose after first dose. These subjects will be considered in the appropriate populations of efficacy analysis for first dose available assessments based on the assumption that they took the second dose after the minimum of 2 hours post first dose. For these subjects any assessments for first dose data after 2 hours will be unscheduled and not be summarized. To rule out this assumption, these subjects will be removed from additional sensitivity analysis as described in Section 11.6 for primary and key secondary analysis.

